5.2 Inclusion criteria

Patients eligible for inclusion in this early treatment protocol have to meet **all** of the following criteria:

1. Prior resection of histologically-diagnosed WHO Grade III or IV glioma.
 - A. Glioma patients who have progressed on or following standard (Stupp regimen) therapy, which included maximal surgical resection, temozolomide, and fractionated radiotherapy.
2. Recurrence must be confirmed by diagnostic biopsy with local pathology review or contrast-enhanced MRI.
3. Subjects must have measurable disease preoperatively, defined as at least 1 contrast-enhancing lesion, with 2 perpendicular measurements of at least 1 cm, as per RANO criteria.
4. For gliomas, archival tissue must demonstrate: (a) RB positivity ($\geq 20\%$) on immunohistochemistry OR no RB mutations on next-generation sequencing (NGS), (b)

Initial Version date: 10/16/2018

Revision date: 03/11/2019, 5/07/2019, 09/26/2019, 03/17/2020, 08/26/2024

Chromosomal loss of CDKN2A/B/C OR CDK4/6 or CCND1/2 amplification on array CGH, (c) mTOR+: PTEN loss OR PIK3C2B or AKT3 amplification on aCGH OR mutations for PIK3CA or PIK3R1, or mTOR or PTEN mutations using rhAMP analysis or pS6 positivity on immunohistochemistry ($\geq 10\%$ for pS6). If mutations within the mTOR/PI3K pathways cannot be accurately detected due to poor tissue quality the enrollment criteria will be determined using RB and pS6 positivity.

5. Eastern Cooperative Oncology Group (ECOG) performance status ≤ 2 ([Appendix 1](#)).
6. Patients ≥ 18 years of age.
7. Ability to understand and the willingness to sign a written informed consent document (personally or by the legally authorized representative, if applicable).
8. Patient has voluntarily agreed to participate by giving written informed consent (personally or via legally-authorized representative(s), and assent if applicable).

(Written informed consent for the protocol must be obtained prior to any screening procedures. If consent cannot be expressed in writing, it must be formally documented and witnessed, ideally via an independent trusted witness.)

9. Willingness and ability to comply with scheduled visits, treatment plans, laboratory tests and other procedures.
10. Confirmed negative serum pregnancy test (β -hCG) before starting study treatment or patient has had a hysterectomy.
11. Patient has adequate bone marrow and organ function as defined by the following laboratory values (as assessed by the local laboratory for eligibility):

The following laboratory criteria have been met:

- Absolute neutrophil count (ANC) $\geq 1.5 \times 10^9/L$ (recommended)
- Hemoglobin (Hgb) $\geq 9.0 \text{ g/dL}$ (Participants may receive erythrocyte transfusions to achieve this hemoglobin level at the discretion of the investigator.)
- Platelets $\geq 100 \times 10^9/L$ (at the time of surgery)
- Potassium, total calcium (corrected for serum albumin), magnesium, sodium, and phosphorus within normal limits for the institution or corrected to within normal limits with supplements before first dose of study medication
- INR ≤ 1.5 (unless the patient is receiving anticoagulants and the INR is within the therapeutic range of intended use for that anticoagulant within 7 days prior to the first dose of study drug)
- Serum creatinine $< 1.5 \text{ mg/dL}$
- Estimated glomerular filtration rate (eGFR) $\geq 50 \text{ mL/min}$
- In the absence of liver metastases, alanine aminotransferase (ALT) and aspartate aminotransferase (AST) $< 2.5 \times \text{ULN}$.
- Serum total bilirubin $\leq \text{ULN}$, or $\leq 3.0 \times \text{ULN}$ in patients with well-documented Gilbert's syndrome
- Serum cholesterol $\leq 300 \text{ mg/dL}$ or $\leq 7.75 \text{ mmol/L}$ AND triglycerides $\leq 2.5 \times \text{ULN}$ (**NOTE:** in case one or both of these thresholds are exceeded, the patient can only be included after initiation of appropriate lipid lowering medication.)

12. QTcF interval at screening $< 450 \text{ msec}$ [using Fridericia's correction (formula = QT/(RR) $^{0.33}$)]

13. Resting heart rate 50-90 bpm (may be repeated up to 2x)
14. Must be able to swallow ribociclib and everolimus capsules/tablets
15. If patient is receiving tamoxifen or toremifene, a washout period of 5 half-lives prior to enrollment is required

5.3 Exclusion criteria

Patients eligible must not meet **any** of the following criteria:

1. Archival tissue is not available for research use or there is not a sufficient quantity available to confirm eligibility.
2. Archival tumor is not Rb-positive status and mTOR-positive status.
3. Patient has not received prior radiotherapy.
4. Co-morbid condition(s) that, at the opinion of the investigator, prevent safe surgical treatment.
5. Active infection or fever $> 38.5^{\circ}\text{C}$ that in the opinion of the investigator would be a safety risk to the patient.
6. Active (acute or chronic) or uncontrolled severe infection, liver disease such as cirrhosis, decompensated liver disease, and active and chronic hepatitis (i.e. quantifiable HBV-DNA and/or positive HbsAg, quantifiable HCV-RNA).
7. Known severely impaired lung function (spirometry and DLCO 50% or less of normal and O₂ saturation 88% or less at rest on room air).
8. Active, bleeding diathesis.
9. Patients with known hypersensitivity to any of the excipients of ribociclib or mTOR inhibitors (sirolimus or everolimus), including peanut, soy and lactose.
10. Patients with a clinically significant hypersensitivity to everolimus or to other rapamycin derivatives.
11. Prior therapy with ribociclib or any CDK4/6 inhibitor (e.g. palbociclib, abemaciclib), or with everolimus. Prior therapy is defined as a therapeutic dosing.
12. Patient who has received radiotherapy ≤ 4 weeks or limited field radiation for palliation ≤ 2 weeks prior to starting study drug, and who has not recovered to grade 1 or better from related side effects of such therapy (exceptions include alopecia or other toxicities not considered a safety risk for the patient at investigator's discretion) and/or in whom $\geq 25\%$ of the bone marrow (Ellis, 1961) was irradiated.
13. Patient has a concurrent malignancy or malignancy within 3 years prior to starting study drug, with the exception of adequately treated, basal or squamous cell carcinoma, non-melanomatous skin cancer or curatively resected cervical cancer.
14. Patient has impairment of gastrointestinal (GI) function or GI disease that may significantly alter the absorption of the study drugs (e.g., ulcerative diseases, uncontrolled nausea, vomiting, diarrhea, malabsorption syndrome, or small bowel resection).
15. Patient has a known history of HIV infection (seropositivity; testing not mandatory).
16. Patients who have received live attenuated vaccines within 1 week of start of everolimus and during the study. Patient should also avoid close contact with others who have received live attenuated vaccines. Examples of live attenuated vaccines include intranasal influenza, measles, mumps, rubella, oral polio, BCG, yellow fever, varicella and TY21a typhoid vaccines.

17. Patient has any other concurrent severe and/or uncontrolled medical condition that would, in the investigator's judgment, cause unacceptable safety risks, contraindicate patient participation in the clinical study or compromise compliance with the protocol (e.g. chronic pancreatitis, chronic active hepatitis, active untreated or uncontrolled fungal, bacterial or viral infections, etc.)
18. Uncontrolled diabetes mellitus as defined by HbA1c >8% despite adequate therapy as indicated by the medical history. Patients with a known history of impaired fasting glucose or diabetes mellitus (DM) may be included, however blood glucose and antidiabetic treatment must be monitored closely throughout the trial and adjusted as necessary.
19. Clinically significant, uncontrolled heart disease and/or cardiac repolarization abnormalities, including any of the following:
 - History of acute coronary syndromes (including myocardial infarction, unstable angina pectoris, coronary artery bypass grafting, coronary angioplasty, or stenting) or symptomatic pericarditis within 6 months prior to screening .
 - History of documented congestive heart failure (New York Heart Association functional classification III-IV).
 - Documented cardiomyopathy.
 - Left Ventricular Ejection Fraction (LVEF) <50% as determined by Multiple Gated acquisition (MUGA) scan or echocardiogram (ECHO) at screening.
 - Clinically significant cardiac arrhythmias (e.g. ventricular tachycardia), complete left bundle branch block, high-grade AV block (e.g. bifascicular block, Mobitz type II and third-degree AV block).
 - Long QT syndrome or family history of idiopathic sudden death or congenital long QT syndrome, or any of the following:
 - Risk factors for Torsades de Pointe (TdP) including uncorrected hypokalemia or hypomagnesemia, history of cardiac failure, or history of clinically significant/symptomatic bradycardia.
 - Concomitant use of medication(s) with a known risk to prolong the QT interval and/or known to cause Torsades de Pointe that cannot be discontinued (within 5 half-lives or 7 days prior to starting study drug) or replaced by safe alternative medication.
 - Inability to determine the QT interval on screening (QTcF, using Fridericia's correction).
 - Systolic blood pressure (SBP) >160 mmHg or <90 mmHg at screening (may be repeated up to 2x).
20. Patient is currently receiving any of the following medications and cannot be discontinued 7 days prior to starting study drug (see [Appendix 2](#) for details):
 - Known strong inducers or inhibitors of CYP3A4/5, including grapefruit, grapefruit hybrids, pomelos/pummelos, star-fruit, pomegranates or pomegranate juice and Seville oranges.
 - That have a narrow therapeutic window and are predominantly metabolized through CYP3A4/5.

- Herbal preparations/medications, dietary supplements known as strong inhibitors or inducers of CYP3A4 or those with a known risk of QT prolongation. (Does not include Ca, Mg, Vit D or KCl supplements).

- Known strong inhibitors or inducers of P-gp.

21. Patients taking ACE inhibitors.
22. Patient is currently receiving warfarin or other coumarin-derived anticoagulant for treatment, prophylaxis or otherwise. Therapy with heparin, low molecular weight heparin (LMWH) or fondaparinux is allowed.
23. Participation in a prior investigational study within 30 days prior to enrollment or within 5 half-lives of the investigational product, whichever is longer.
24. Patient has had major surgery within 14 days prior to starting study drug or has not recovered from major side effects (tumor biopsy is not considered as major surgery).
25. Patient has not recovered from all toxicities related to prior anticancer therapies to NCI-CTCAE version 4.03 Grade ≤ 2 (Exception to this criterion: patients with grade 1 taxane-induced neuropathy, any grade of alopecia, amenorrhea or other toxicities not considered a safety risk for the patient as per investigator's discretion, are allowed to enter the study.).
26. Patient with a Child-Pugh score B or C.
27. Patient has a history of non-compliance to medical regimen or inability to grant consent.
28. Pregnant or nursing (lactating) women, where pregnancy is defined as the state of a female after conception and until the termination of gestation, confirmed by a positive hCG laboratory test.
29. Women of child-bearing potential, defined as all women physiologically capable of becoming pregnant, **unwilling to use** highly effective methods of contraception during dosing and for 3 months after the last dose of study treatment. Highly effective contraception methods include:
 - Total abstinence (when this is in line with the preferred and usual lifestyle of the subject. Periodic abstinence (e.g., calendar, ovulation, symptothermal, post-ovulation methods) and withdrawal are not acceptable methods of contraception.
 - Female sterilization (have had surgical bilateral oophorectomy with or without hysterectomy) or tubal ligation at least six weeks before taking study treatment. In case of oophorectomy alone, only when the reproductive status of the woman has been confirmed by follow up hormone level assessment.
 - Male sterilization (at least 6 months prior to screening) with the appropriate post-vasectomy documentation of the absence of sperm in the ejaculate. For female subjects on the study the vasectomized male partner should be the sole partner for that subject.
 - Use of oral, injected or implanted hormonal methods of contraception or placement of an intrauterine device (IUD) or intrauterine system (IUS), or other forms of hormonal contraception that have comparable efficacy (failure rate $<1\%$), for example, hormone vaginal ring or transdermal hormone contraception.
 - In case of use of oral contraception, women should have been stable on the same pill for a minimum of 3 months before taking study treatment.
 - Note: Oral contraceptives are allowed but should be used in conjunction with a barrier method of contraception due to unknown effect of drug-drug interaction.

Women are considered post-menopausal and not of child bearing potential if they have had 12 months of natural (spontaneous) amenorrhea with an appropriate clinical profile (e.g. age appropriate history of vasomotor symptoms) or have had surgical bilateral oophorectomy (with or without hysterectomy) or tubal ligation at least six weeks ago. In the case of oophorectomy alone, only when the reproductive status of the woman has been confirmed by follow up hormone level assessment is she considered not of child bearing potential.

30. Sexually active males unwilling to use a condom during intercourse while taking drug and for 21 days after stopping treatment and should not father a child in this period. A condom is required to be used also by vasectomized men in order to prevent delivery of the drug via seminal fluid.

6 Treatment

6.1 Protocol treatment

For this protocol, the term “treatment” refers to ribociclib+everolimus.

Table 6 Dose and treatment schedule

Study treatments	Pharmaceutical form and route of administration	Dosage Form and Strength	Frequency and/or Regimen
Phase 0			(5 day regimen)
Ribociclib (LEE011)	Tablet for oral use	200mg tablets 2.5mg tablet	Once daily
Everolimus	Tablet for oral use		Once daily or Twice daily*
Phase 2 (optional)			(28 day cycle)
Ribociclib (LEE011)	Tablet for oral use	200mg tablets 2.5mg tablet	Once daily for 3 weeks, 1 week off
Everolimus	Tablet for oral use		Once daily* or Twice daily** for 3 weeks, 1 week off

*Dose Level 4+: everolimus is taken once on Day 5 in Phase 0. In Phase 2, everolimus dose will be given weekly on Days 1, 8, 15, 22 of each cycle.

**Dose Level 3: everolimus is taken twice daily in Phase 2.

6.1.1 Phase 0 & 2 Dose Escalation Schedule

Table 7 Dose Escalation Schedule

Dose Level	Phase 0 Dose of Study Drug ^a	Minimum Number of Patients	Phase 2 Dose of Study Drug ^a
0	ribociclib 400mg and everolimus 2.5mg	6	ribociclib 400mg and everolimus 2.5mg
1	ribociclib 600mg and everolimus 2.5mg	3	ribociclib 600mg and everolimus 2.5mg

Initial Version date: 10/16/2018

Revision date: 03/11/2019, 5/07/2019, 09/26/2019, 03/17/2020, 08/26/2024

Dose Level	Phase 0 Dose of Study Drug ^a	Minimum Number of Patients	Phase 2 Dose of Study Drug ^a
2	ribociclib 600mg and everolimus 5mg	3	ribociclib 600mg and everolimus 5mg
3	ribociclib 600mg and everolimus 10mg ^b	3	ribociclib 600mg and everolimus 10mg ^c
4	ribociclib 600mg, qd and everolimus 50mg once ^d	3	ribociclib 600mg daily and everolimus 50mg once weekly ^e
5	ribociclib 600mg, qd and everolimus 60mg once ^d	3	Cycle 1: ribociclib 600mg, qd and everolimus 50mg once weekly ^e Cycle 2+: 600 mg, qd and everolimus 60mg once weekly ^f
6	ribociclib 600mg, qd and everolimus 70mg once ^d	3	Cycle 1: ribociclib 600mg, qd and everolimus 50mg once weekly ^e Cycle 2: 600 mg, qd and everolimus 60mg once weekly ^f Cycle 3+: 600 mg, qd and everolimus 60mg once weekly ^f

- a. The Phase 0 dose given to the patient will be the RP2D. If more than one DLT is observed in 6 patients in Phase 2, the regimen at that given level will be considered as the maximal administered dose and the next lower dose level will be the MTD/RP2D for subsequent patients enrolled into Phase 2
- b. In Phase 0, the everolimus dose will be given in one dose (10mg, qd).
- c. In Phase 2, dose will be given in two doses (5mg, bid)
- d. In Phase 0, the everolimus dose will be given in one dose on Day 5 only; ribociclib dose will be given daily for 5 days.
- e. In Phase 2, everolimus dose will be given once weekly on Days 1, 8, 15, 22 of each cycle with ribociclib administered daily for 21 consecutive days and 1 rest week.
- f. If the dose is well tolerated in Cycle 1, the dose may be escalated based on investigator discretion.

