Due to persistent negative PK effects from everolimus, despite no adverse events limiting drug dosing, additional dose-levels will employ a single, high-dose administration of everolimus. Other combination drug studies have suggested 70mg weekly as a maximal-tolerated dose. As a lead-in to this combination dose in our study, a new dose level at 50mg once prior to surgery (in combination with 600mg ribociclib) will be introduced. This lead-in dose will give rise to 60mg at the next level and 70mg at the final level. Similarly, the phase 2 component of the study will reflect this new dosing regimen for patients with PK and PD effects from both drugs. Specifically, a lead-in regimen at 50mg q weekly in Phase 2 (in combination with ribociclib) will then be escalated towards 70mg weekly.

3 Objectives and endpoints

	Objective	Endpoint
Primary	
• To determine the dose-limiting toxicity (DLT) and maximum tolerated dose (MTD) for study drug when administered in combination.• To identify recurrent high-grade glioma patients with positive PK and PD effects.	
• MTD: highest dose of drug that did not cause a DLT in > 17% of participants• PK: total and unbound ribociclib and everolimus concentrations in non-enhancing and contrast-enhancing tumor tissue samples• PD: pRB-positive cells and pS6-positive cells
Secondary	
• To explore safety and efficacy in recurrent high-grade glioma patients with demonstrated PK and PD effects and determine RP2D• To describe PK for Phase 2 patients	
• Progression-free survival (PFS)• Overall survival (OS)• Drug-related toxicity• RP2D• Systemic PK profiles of ribociclib and everolimus when combined.
Exploratory	
• To explore evidence for CDK4/6 and mTOR pathway activity in tumor tissue (as compared to	
• Quantification of total and phosphorylated forms of Rb, FoxM1, S6, 4EBP, as well as cleaved Caspase-3 and MIB1. Expression of Cyclin D1,

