4.1.2 Phase 2 Dose expansion

Patients with tumors demonstrating favorable PK and PD will proceed to Phase 2 Dose Expansion. In Dose Levels 1-3, patients will continue treatment with the same treatment level as given in Phase 0, patients should take the treatment continuously in 28d cycles with 3 weeks on / 1 week off after surgery. In Dose Level 4+, patients should take everolimus in one dose weekly; ribociclib will be taken for 21 consecutive days followed by 1 rest week. The dose will be per Table 7. If more than one DLT is observed in 6 patients in the Phase 2 dose expansion, the enrollment will be stopped and the previous lower dose level will be considered the RP2D and will be given for the remaining patients enrolled. If more than one DLT is occurred with the Level 0, the study will be stopped due to toxicity. Typically DLTs are defined by 1 cycle of treatment, which is 28 days. Since Phase 0 treatment is given for only 5 days, Phase 0 dose escalation will only be determined by Phase 0 DLT rules unless determined otherwise by the DSMB. Patients will be treated until unacceptable toxicity is observed, or until disease progression as assessed by radiographic or clinical metrics. Preliminary rates of progression-free survival in patients with high-grade gliomas treated with ribociclib+everolimus will be measured through radiographic and clinical response metrics, specifically Response Assessment in Neuro-Oncology (RANO) criteria and investigator discretion. Phase 2 participants will return to the clinic to monitor safety per the schedule of events until treatment is ended and will then be contacted approximately every 3 months by letter or phone for collection of survival data. The start of follow up for long-term survival begins following completion of the Day 30 safety follow up call.. All Phase 0/2 participants will be followed for survival for up to 5 years.

Common Toxicity Criteria Adverse Event (CTC AE 4.03) will be utilized to review ribociclib+everolimus treatment effects in patients with brain tumors.

Trough steady-state blood samples will be obtained on days 1, 8, 15, and 22 of cycles 1 and 2 prior to the administration of ribociclib+everolimus on that day. Note: ribociclib+everolimus will be administered in the clinics on the clinic visit days to ensure the collection of trough level samples.

PHASE 2 STUDY				
	Cycle 1 (28 d)	Cycle 2 (28d)	Subsequent cycles (28d)	End of study
Day of cycle	D1, D8, D15, D22	D1, D8, D15, D22	N/A	N/A

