6.2.2 Dose modification and dose delay of ribociclib+everolimus

Guidelines for dose, modifications, interruptions and re-initiation of ribociclib+everolimus treatment are described in [Table 11](#). The following are the dose modification levels in [Table 10](#).

Table 10 Dose Modification Levels

Ribociclib	
Dose	Number of tablets & strength
200 mg (qd)*	1 x 200 mg tablet
400 mg (qd)	2 x 200 mg tablet
600 mg (qd)	3 x 200 mg tablet

* One dose de-escalation will be allowed below dose level 0 if needed as a dose modification.

Everolimus	
Dose	Number of tablets & strength
2.5 mg every other day (qod)*	1 x 2.5 mg tablet
2.5 mg daily (qd)	1 x 2.5 mg tablet
5 mg daily (qd)	2x 2.5 mg tablet
10 mg (qd)	4x 2.5 mg tablet

Everolimus- for Dose Levels 4-6 and possible dose reductions	
Dose	Number of tablets & strength
25 mg (1/weekly) – 50% of dose level 4	2 x 10 mg tablet and 2 x 2.5mg tablet
30 mg (1/weekly) - 50% of dose level 5	3 x 10 mg tablet
35 mg (1/weekly) - 50% of dose level 6	3 x 10 mg tablet and 2 x 2.5mg tablet
40 mg (1/weekly) – 1 dose reduction from dose level 4	4 x 10 mg tablet
50 mg (1/weekly) – 1 dose reduction from dose level 5	5 x 10 mg tablet
60 mg (1/weekly) – 1 dose reduction from dose level 6	6 x 10 mg tablet
70 mg (1/weekly)	7 x 10 mg tablet

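### Table 7 never schedules 70 mg weekly everolimus at Level 6, and Tables 10 and 11 leave the reduced everolimus dose unclear at Levels 4 to 6

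*Combined protocol and SAP*

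**What the plan says.** Section 4.1.2 says of Phase 2 dosing at Level 4 and above: "The dose will be per Table 7". In Table 7 (Section 6.1.1), Levels 5 and 6 both start at 50 mg weekly in Cycle 1. Level 5 then has "Cycle 2+: 600 mg, qd and everolimus 60mg once weekly". Level 6 has 60 mg in Cycle 2 and then "Cycle 3+: 600 mg, qd and everolimus 60mg once weekly". Ribociclib is 600 mg daily at both levels. Footnote f, attached to the 60 mg entries, lets the investigator escalate if Cycle 1 is well tolerated, but names no dose.

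Section 2.3 describes the intention differently: "a lead-in regimen at 50mg q weekly in Phase 2 (in combination with ribociclib) will then be escalated towards 70mg weekly". Table 10 (Section 6.2.2) has a 70 mg weekly row, sets 35 mg as half of Level 6, and labels its one-step rows by level: "60 mg (1/weekly) – 1 dose reduction from dose level 6" and "50 mg (1/weekly) – 1 dose reduction from dose level 5".

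Table 11 (Section 6.2.3) restarts everolimus one dose level down, with no size given, in four entries: grade 4 neutropenia, grade 3 febrile neutropenia, and grade 3 and grade 4 thrombocytopenia. In the grade 3 row for all other adverse reactions, the same instruction carries a gloss of 50% of the previous dose. A closing note to Table 11 suggests a dose about half of the one last given.

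If more than one of 6 Phase 2 patients has a DLT, Section 4.1.2 says that "the previous lower dose level will be considered the RP2D and will be given for the remaining patients enrolled". Footnote a to Table 7 agrees: "the next lower dose level will be the MTD/RP2D for subsequent patients enrolled into Phase 2".

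**The concern.** The controlling dose table contradicts the rationale and the dose-reduction table on the top dose of the trial. A separate Cycle 3+ line for Level 6 serves no purpose if the dose stays where it was in Cycle 2. A site following Table 7 would give Level 6 patients the Level 5 regimen throughout, and the report could describe a Level 6 experience that never included scheduled 70 mg weekly dosing. RP2D is a secondary endpoint, so this matters for what the trial can say about that dose.

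The reduction rules are a safety matter. Under Section 6.2.1, neutropenia and thrombocytopenia are the only grade 4 toxicities after which study treatment may resume, so the restart dose should be plain there. In three of the four entries ribociclib also goes down a level, which gives some protection. At a first grade 3 thrombocytopenia ribociclib restarts unchanged, so the everolimus step is the whole reduction.

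**Working it through.** **Inputs.** Scheduled weekly doses come from Table 7. One-step and 50% rows come from Table 10. The suggested halving comes from the closing note to Table 11. Weekly dosing falls on Days 1, 8, 15 and 22 (Table 7, footnote e), so there are 4 doses per cycle.

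**1. What Table 10 takes each level to be.** Twice the 50% row: 2 × 25 = 50 mg (Level 4), 2 × 30 = 60 mg (Level 5), 2 × 35 = 70 mg (Level 6). The one-step row plus the 10 mg step: 40 + 10 = 50, 50 + 10 = 60, 60 + 10 = 70 mg. The two agree. They match the highest Table 7 dose for Levels 4 and 5 (50 and 60 mg), but not for Level 6 (60 mg printed, 70 mg implied).

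**2. Level 6 against Level 5, mg per cycle.**

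| Cycle | Level 5 | Level 6 as printed | Level 6 if Cycle 3+ is 70 mg |
|---|---|---|---|
| 1 | 4 × 50 = 200 | 200 | 200 |
| 2 | 4 × 60 = 240 | 240 | 240 |
| 3+ | 240 | 240 | 4 × 70 = 280 |

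As printed the difference is 0 in every cycle. With 70 mg it is 40 mg per cycle from Cycle 3 (40/280 = 14.3%).

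**3. Table 10 one-step label against the dose being taken.**

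| Level, cycle | Dose taken (mg) | One-step label (mg) | Change (mg) |
|---|---|---|---|
| 4, all | 50 | 40 | −10 |
| 5, Cycle 1 | 50 | 50 | 0 |
| 5, Cycle 2+ | 60 | 50 | −10 |
| 6, Cycle 1 | 50 | 60 | +10 |
| 6, Cycle 2 | 60 | 60 | 0 |
| 6, Cycle 3+ as printed | 60 | 60 | 0 |
| 6, Cycle 3+ at 70 mg | 70 | 60 | −10 |

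Correcting the Table 7 cell repairs only the Level 6 Cycle 3+ row. The 50% rows are tied to the nominal level in the same way. They do lower a 50 mg lead-in dose, but by less than half: 30/50 is a 40% cut and 35/50 a 30% cut.

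**4. One step or half, in the four hematologic entries.**

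| Dose taken (mg) | One 10 mg step | About half | Gap per cycle |
|---|---|---|---|
| 50 | 40 mg (−20%) | 25 mg (−50%) | 4 × (40 − 25) = 60 mg |
| 60 | 50 mg (−16.7%) | 30 mg (−50%) | 4 × (50 − 30) = 80 mg |

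The first line is exactly Table 10's pair for Level 4 (40 and 25 mg). Level 4 has no lead-in, so this ambiguity does not come from the keying in step 3. It applies to Levels 4, 5 and 6 alike.

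**The case against.** **Footnotes.** Footnote f permits escalation beyond the printed doses, and footnote a calls the Phase 0 dose (70 mg at Level 6) the RP2D. Both fit an intention to reach 70 mg. Neither schedules it: footnote f is a discretionary permission with no dose, and footnote a sets no cycle. Section 2.3 says only towards 70 mg. The 60 mg entry is probably a slip, but it stands in the table that sites are told to follow.

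**Closing note to Table 11.** It refers to the dose previously given, not the nominal level, and is not confined to non-hematologic events. Applied as a rule, it would give 25 mg from 50 mg and 30 mg from 60 mg. That carries weight. But it is worded as a suggestion, and Table 10 keeps separate one-step and 50% rows; if halving always governed, the one-step rows would have no use.

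**Step-down.** A reader might infer that the 60 mg cell is what makes a step-down from Level 6 to Level 5 empty. The documents do not support that. Section 6.1.3 counts Phase 2 DLTs in the first 28-day cycle, when Levels 4, 5 and 6 all receive 50 mg weekly. Correcting the cell leaves Cycles 1 and 2 identical across Levels 5 and 6 and changes the step-down only from Cycle 3 (280 against 240 mg per cycle).

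**Dose increase.** A reader might also infer that Table 10 would raise a Level 6 patient from 50 to 60 mg after toxicity. That is unlikely in practice, because Table 11 calls for a lower level and its closing note points to about half.

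**Reach.** Reaching the 60 mg cell requires escalation to Level 6, positive PK and PD, and treatment into Cycle 3. Section 2.3 reports persistently negative everolimus PK at earlier doses, so entry is uncertain. This limits the severity.

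**Conclusion.** Three separate defects stand.

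1. Table 7 gives Level 6 the same Phase 2 regimen as Level 5 (50, 60, 60 mg) and never schedules 70 mg weekly, against Section 2.3 and Table 10. That 70 mg was meant is an inference from those two places; a 60 mg cap cannot be ruled out.
2. Table 10's one-step labels do not lower the dose in Level 5 Cycle 1, Level 6 Cycle 1 or Level 6 Cycle 2, nor in Level 6 Cycle 3+ while that cell reads 60 mg.
3. Independently of the keying, and at Levels 4 to 6 alike, four everolimus entries in Table 11 leave open a choice worth 60 mg per cycle from a 50 mg dose and 80 mg from a 60 mg dose.

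Severity is minor to moderate. Section 9.7.1 expects at most 12 Phase 2 patients over all levels. The Table 7 slip errs towards the lower dose, and no sample-size or power figure depends on it. Grade 3 anemia and grade 3 neutropenia restart everolimus at the same dose and are not affected.

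**What to change.** 1. In Table 7, set Level 6 Cycle 3+ to 70 mg weekly. If 60 mg is the intended cap, say so, remove the 70 mg weekly row from Table 10 and correct its Level 6 rows.
2. Tie Table 10 reductions to the dose being taken: one step is 70 to 60, 60 to 50 or 50 to 40 mg; 50% is half the current dose (35, 30 or 25 mg). Add a further step, or discontinuation, for recurrence: Table 11 asks for another everolimus reduction if grade 3 thrombocytopenia recurs, and the weekly ladder has no one-step row below 40 mg.
3. In the four hematologic everolimus entries of Table 11, state for Levels 4 to 6 whether the reduction is one step or about half. The choice is clinical and belongs to the sponsor and the DSMB.

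The cost is an amendment to one cell of Table 7, the weekly everolimus rows of Table 10 and four short glosses in Table 11. No new data, visits or patients are needed. These edits will not make a step-down among Levels 4 to 6 change the Cycle 1 dose, because the shared 50 mg lead-in is part of the design.
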